of activity at 45mg, even if well tolerated, potentially lower doses (eg 30mg) may also be explored in the FGFR1 cohorts to mitigate safety in future studies. The National Cancer Institute Common Terminology Criteria for Adverse Events (NCI-CTCAE, Version 4.0) will be used to grade adverse events. A dose level will be considered tolerable following completion of 1 cycle (28 days) in 9 of 12 patients in the absence of dose limiting toxicity (DLT). If ≥ 3 patients experience DLT at this dose level, the dose level will be deemed non-tolerated. A DLT will be defined by the adverse events listed in Section 9 that are considered possibly, probably, or definitely related to ponatinib. If 45mg is not tolerated per DLT criteria, 30mg will be explored in the FGFR1 cohorts, assuming insufficient patients were treated at 45mg to assess efficacy accurately. As the IC50 for RET is an order of magnitude lower than for FGFR1, and the starting dose for the RET cohort will be 30mg, the logic relating to efficacious exposures for doses based on FGFR1 PD markers/responses will not automatically be applied to the *RET+* cohort and if activity in *RET+* cases is noted at the time this will not influence the decision-making re dose alteration in the *FGFR1+* cohorts. However, if ≤ 2 responses are seen in the initial *RET+* cohort but *FGFR1+* responses or FGFR PD modulation have been noted at 45mg and 45mg appears acutely well tolerated per DLT criteria we will reconsider this logic and accrue an additional *RET+* cohort at 45mg. If doses other than 45mg QD are explored, the number of patients in each biomarker selected cohort will be modified to include only those treated at the final ‘biologically selected dose’ (i.e. the tolerable dose associated with evidence of FGFR pathway pharmacodynamic modulation or of radiographic responses in FGFR biomarker selected cohorts) and the response rates in each biomarker selected cohort will be calculated within each cohort using only the number treated at this dose.

Objectives:

Primary:

Part A – To determine the prevalence of defined biomarkers in the screened patient populations.

Part B –To determine the objective response rate (ORR) (RECIST v1.1) to ponatinib in different molecularly defined cohorts of lung cancer.

Secondary:

Part A –

- 1) To determine the effectiveness of prescreening locally and nationally.
- 2) To determine the clinical and pathological features associated with biomarker positivity and negativity.

Part B –

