Another role of the double negative cohort is to permit rapid patient accrual to assess the PD/dose determination markers early in the conduct of the study, being expanded as needed if doses less than 45mg QD have to be explored. In addition, it may generate 'atypical' *RET* and *FGFR1* negative responders, to be further explored in future.

The proportion of the initial 12 patients at 45mg QD (and in the 12 patients at any subsequent dose levels) demonstrating a $\geq 50\%$ increase in plasma FGF23 by Day15 (defined as a 'PD-response') will be assessed in the same statistical manner as radiographic responses in order to determine whether the dose/regimen used is affecting the FGFR pathway in normal tissues. A $\geq 50\%$ increase in plasma FGF23 measurements occurring in ≥ 3 of 12 patients will be considered indicative of FGFR inhibition (Shi et al, 2009). In addition, FGFR inhibition should be accompanied with a decrease in the fractional excretion of phosphorus in the urine (normal: 10-15%) and an elevation of serum phosphorus compared to baseline at the same time. If exposures are inadequate to affect these biomarkers (provided no evidence of tumor shrinkage has occurred in any of the FGFR+ cohorts by that point), higher doses/exposure regimens will not be explored. If 45mg is not-tolerated and insufficient patients treated to accurately assess efficacy, 30mg may be explored in the FGFR1 and double negative cohorts.

If doses other than 45mg QD have to be explored, the number of patients in each biomarker selected cohort will be modified to include only those treated at the final dose and the response rates in each biomarker selected cohort will be calculated within each cohort using only the number treated at this dose. The number of adverse events and percentages will be tabulated per organ and per visit. Kaplan-Meier survival curves will be used to display PFS and extra-CNS PFS (Camidge et

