responses are seen in the initial RET+ cohort but FGFR1+ responses or FGFR PD modulation have been noted at 45mg and 45mg appears acutely well tolerated per DLT criteria we will reconsider this logic and accrue an additional RET+ cohort at 45mg. If doses other than 45mg QD are explored, the number of patients in each biomarker selected cohort will be modified to include only those treated at the final ‘biologically selected dose’ (i.e. the tolerable dose associated with evidence of FGFR pathway pharmacodynamic modulation or of radiographic responses in FGFR biomarker selected cohorts) and the response rates in each biomarker selected cohort will be calculated within each cohort using only the number treated at this dose.

Objectives:

Primary:

Part A – To determine the prevalence of defined biomarkers in the screened patient populations.

Part B – To determine the objective response rate (ORR) (RECIST v1.1) to ponatinib at a ‘biologically selected dose’ in different molecularly defined cohorts of lung cancer.

Secondary:

Part A –

- 1) To determine the effectiveness of prescreening locally and nationally.
- 2) To determine the clinical and pathological features associated with biomarker positivity and negativity.

Part B –

- 1) To evaluate the safety, tolerability, and adverse event profile of ponatinib in patients with advanced lung cancer.
- 2) To determine the progression free survival (PFS), pattern of failure (CNS vs. extra-CNS) and response duration (in patients who achieve an objective response) of ponatinib in molecularly defined cohorts of patients with advanced lung cancer treated at the ‘biologically selected dose’.
- 3) To compare the ORR in biomarker positive cohorts to the FGFR1 double negative cohort.

Tertiary/Exploratory:

- 1) To explore additional molecular mechanisms of initial sensitivity and resistance to ponatinib in patients with advanced lung cancer, including but not limited to addressing the impact of higher cutpoints/alternate patterns of FGFR1 copy number by SISH and mRNA levels by ISH on maximal percentage shrinkage per RECIST or PFS or duration of response in the FGFR1 copy number and/or mRNA positive cohorts; and the impact of FGF2 and/or 9 ligand mRNA levels by ISH on maximal percentage shrinkage per RECIST or PFS or duration of response in FGFR1 copy number and/or mRNA positive cohorts.

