Patients must complete 24 of the planned 28 days (85%) dosing of ponatinib in Cycle 1 to be evaluable in the absence of DLTs. If not evaluable for the purposes of determination of drug tolerability, the patient may continue to be treated, but will be replaced if needed to determine adequate numbers for tolerability and dose decision making.

As the IC50 for RET is an order of magnitude lower than for FGFR1, RET cohorts will commence at 30mg and the logic relating to efficacious exposures for doses based on FGFR1 PD markers/responses will not automatically be applied to the *RET*+ cohort and if activity in *RET*+ cases is noted at the time this will not influence the decision-making re dose alteration in the *FGFR1*+ cohorts. However, if ≤ 2 responses are seen in the initial *RET*+ cohort but *FGFR1*+ responses or FGFR PD modulation have been noted at 45mg and 45mg appears to be acutely well tolerated per DLT criteria we will reconsider this logic and accrue an additional *RET*+ cohort at 45mg. If no evidence of FGFR pathway modulation or of clinical benefit has been seen in *FGFR*+ cases across all achievable alternative doses, accrual to

FGFR1+ cohorts will be suspended. If doses other than 45mg QD are explored, the number of patients in each biomarker selected cohort will be modified to include only those treated at the final ‘biologically selected dose’ (i.e. the tolerable dose associated with evidence of FGFR pathway pharmacodynamic modulation or of radiographic responses in FGFR biomarker selected cohorts) and the response rates in each biomarker selected cohort will be calculated within each cohort using only the number treated at this dose.

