2009). In addition, FGFR inhibition should be accompanied with a decrease in the fractional excretion of phosphorus in the urine (normal: 10-15%) and an elevation of serum phosphorus compared to baseline at the same time. If exposures are inadequate to affect these biomarkers (provided no evidence of tumor shrinkage has occurred in any of the FGFR+ cohorts by that point), due to the new data on risk factors associated with ponatinib, higher doses/dosing regimens of ponatinib will not be explored, however, if 45mg is not tolerable, but there is insufficient evidence to assess efficacy, 30mg will be considered for exploration in the FGFR-related cohorts. RET patients will commence at 30mg from the start due to the higher potency for ponatinib towards RET. A dose level will be considered tolerable following completion of 1 cycle (28 days) in 9 of 12 patients in the absence of dose limiting toxicity (DLT). If ≥ 3 patients experience DLT at this dose level, the dose level will be deemed non-tolerated.

If doses other than 45mg QD have to be explored, the number of patients in each biomarker selected cohort will be modified to include only those treated at the final 'biologically selected dose' (i.e. the dose associated with evidence of FGFR pathway PD modulation or of radiographic responses in FGFR+ cohorts) and the response rates in each biomarker selected cohort will be calculated within each cohort using only the number treated at this dose. The number of adverse events and percentages will be tabulated per organ and per visit. Kaplan-Meier survival curves will be used to display PFS and extra-CNS PFS (Camidge et al, 2011; Lin et al, 2012). Progression-free median time and 95% confidence interval will be reported. Proportions of failure due to CNS or extra-CNS will be reported along with 95% exact confidence intervals. Response duration will be summarized using median and range (min, max). Where biomarker overlap occurs, exploratory analyses of the differential effect of one biomarker over another will be explored across patients in all cohorts using multivariate analysis. Exploratory analyses will include assessing the impact of different SISH+ patterns, of higher cutpoints for FGFR1 SISH and ISH and the impact of FGF ligand levels on maximal percentage shrinkage per RECIST or PFS or duration of response in the FGFR1 SISH/ISH+ cohorts.

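### The final-dose rule is defined by FGFR evidence alone and does not exempt RET+, so under stated conditions it drops the 30mg RET+ patients from their own response rate

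*Combined protocol and SAP*

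**What the plan says.** Section 9.2 plans 45mg for the FGFR-related cohorts and 30mg for RET+. It also allows 30mg in the FGFR cohorts, either because 45mg is not tolerated and efficacy data are too few, or by choice once 45mg is tolerated and shows activity.

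The rule that sets each cohort's response denominator appears in six places.

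- Section 9.3: "If doses other than 45mg QD are explored, the number of patients in each biomarker selected cohort will be modified to include only those treated" with one final dose, defined there as "the tolerable dose associated with evidence of FGFR pathway pharmacodynamic modulation or of radiographic responses in FGFR biomarker selected cohorts". The synopsis paragraph describing Part B, Section 1 and Section 4.0 say the same.
- Section 10.3: "If doses other than 45mg QD have to be explored, the number of patients in each biomarker selected cohort will be modified to include only" patients at the final dose, here "the dose associated with evidence of FGFR pathway PD modulation or of radiographic responses in FGFR+ cohorts".
- The synopsis Part B Analysis Plan uses the Section 10.3 trigger and a shortened rule: each cohort "will be modified to include only those treated at the final dose and the response rates" follow from that.

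The only RET-specific text near the rule, in Section 9.3, is that "the logic relating to efficacious exposures for doses based on FGFR1 PD markers/responses will not automatically be applied to the" RET+ cohort.

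The primary objective also differs. The synopsis has no dose limit: "To determine the objective response rate (ORR) (RECIST v1.1) to ponatinib in different molecularly defined cohorts of lung cancer". Section 1 has one: "To determine the objective response rate (ORR) (RECIST v1.1) to ponatinib at a" biologically selected dose. Secondary objective 2 (progression-free survival, pattern of failure, response duration) carries the dose limit in both places.

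**The concern.** The rule covers every biomarker selected cohort, and Section 1 uses that term for a set that includes RET+. The selected dose, however, is identified only from FGFR evidence, and RET+ starts at a different dose from the FGFR1 cohorts. When the rule operates and the FGFR evidence points to 45mg, the literal text leaves no patient from the planned RET+ cohort in the RET+ response set. The 3-of-12 decision for that cohort then has nothing to act on, and its progression-free survival and response duration under secondary objective 2 go the same way.

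Whether the rule operates depends on which section is followed, because the trigger is not the same throughout. In an open-label trial whose decision turns on 3 responses in 12, the denominator should not be left to a choice made after responses are known.

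**Working it through.** **1. The plan's own figure.** Section 10.3: n = 12, reject the null at 3 or more responses, p0 = 0.05, p1 = 0.40.

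- Type I error = 1 − [0.95^12 + 12(0.05)(0.95^11) + 66(0.05²)(0.95^10)] = 1 − (0.5404 + 0.3413 + 0.0988) = 0.0196. The plan states 0.02.
- Power = 1 − [0.6^12 + 12(0.4)(0.6^11) + 66(0.4²)(0.6^10)] = 1 − (0.0022 + 0.0174 + 0.0639) = 0.9166. The plan states over 90%.

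Both are reproduced. The question is which patients form the 12.

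**2. The texts side by side.**

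| Place | Trigger | Selected dose | RET+ exempt? |
|---|---|---|---|
| Synopsis (Part B paragraph), Sections 1, 4.0, 9.3 | other doses *are explored* | tolerable dose with FGFR evidence | no |
| Section 10.3 | other doses *have to be explored* | dose with FGFR evidence | no |
| Synopsis, Part B Analysis Plan | other doses *have to be explored* | final dose | no |
| Section 1 primary objective; secondary objective 2 | none | biologically selected dose | no |

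**3. The routes.**

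- *30mg by choice in the FGFR1 cohorts (Section 9.2).* This requires 45mg to be tolerated with radiographic or pharmacodynamic evidence, so 45mg already meets the Section 9.3 definition. The Section 9.3 trigger is met; the Section 10.3 trigger is not plainly met. With 45mg selected, Section 9.3 keeps 0 of the 12 RET+ patients, whereas Section 10.3, if not triggered, keeps all 12. If 30mg also qualifies and is called final, RET+ stays in. No tie-break is given.
- *An additional RET+ cohort at 45mg (Sections 4.0, 9.3).* This requires at most 2 responses at 30mg, FGFR1 responses or FGFR modulation at 45mg, and tolerability at 45mg, so again 45mg meets the definition. RET+ then has patients at two doses, and no text says whether the 30mg patients remain in its response rate. The response part of the condition, P(X ≤ 2 | 12, p), is 0.083 at p = 0.40, and 0.253 or 0.558 at an assumed p of 0.30 or 0.20.
- *The planned 30mg start read as exploration.* Sections 7.3 and 9.3 both state the RET+ start under headings about dosing other than 45mg, and Section 7.2 speaks of cohorts other than RET exploring 30mg. Against this, Section 9.2 calls 30mg the planned RET+ dose.
- *45mg not tolerated, 30mg explored and selected.* Both triggers are met, and all 12 RET+ patients stay in.

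**4. The objectives.** The Section 1 primary objective and secondary objective 2 need no trigger. If 45mg is the FGFR-selected dose, they literally do not cover a cohort treated at 30mg.

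**The case against.** The strongest reply is that the intent is plain. Section 9.3 counts responses in the initial RET+ cohort against a cut of 2, which is the 3-of-12 rule applied at 30mg. Section 10.1 sizes a 13-patient RET+ cohort, and Section 10.3 applies the design to each positive cohort and reports response by dose with exact intervals. The sentence limiting FGFR logic for RET+ sits in the same paragraph as the rule. All of this stands as evidence of intent. But that sentence concerns exposures and dose choice, and neither the analysis-set rule nor the objectives repeat it. The intent supports the correction; it does not make the text say it.

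Four stronger inferences are not supported.

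- A reader might infer that the plan excludes RET+ as it stands, with 0 patients under Section 9.3 against 12 under Section 10.3. Sections 7.3 and 9.2 support reading 30mg as planned rather than explored, so the rule need not operate at all.
- A reader might infer that Section 10.3 could select an untolerated dose because it omits *tolerable*. The DLT criterion is stated immediately before the rule, so the omission has little effect.
- A reader might use the Table 10 yields to project a very small 45mg RET+ set. That would be an accrual projection, resting on failure at 30mg, rounded yields, no added sites and discarding the 30mg data. It does not measure this defect.
- A reader might infer that the FGFR1 decisions lose error control if either dose could supply the 12. With two independent full sets the chance of at least one false positive is 1 − (1 − 0.0196)² = 0.0388, below the 5% target.

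**Conclusion.** Wrong as written, conditionally. A rule that sets the primary analysis population for every biomarker cohort is defined by FGFR evidence alone and does not exempt the cohort dosed on different grounds. When it is triggered and 45mg is selected, it removes all 12 evaluable 30mg RET+ patients; when 30mg is selected, it removes none. The clearest trigger is the discretionary 30mg exploration in Section 9.2, where 45mg qualifies by the terms of entry. Even without a trigger, the Section 1 primary objective and secondary objective 2 impose the same dose limit, so response rate, progression-free survival and response duration for one of five cohorts are affected.

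This rests on reading the rule literally and on 45mg being the selected dose, which Section 1 makes likely by predicting adequate FGFR1 exposure at 45mg. The sample size, type I error and power are sound. Which dose carries the FGFR1 decision after optional 30mg exploration is a secondary, contingent matter. The correction is worth making before responses are known.

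**What to change.** Use one text in all six places (both synopsis passages and Sections 1, 4.0, 9.3 and 10.3).

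1. Limit the rule to the FGFR1 and double negative cohorts, with the single trigger *have to be explored*.
2. State that RET+ response rate, progression-free survival and response duration are analysed at 30mg, with the 3-of-12 rule for response. Any additional 45mg RET+ cohort is analysed separately and does not replace the first. The text should also say whether that cohort carries its own 3-of-12 decision; if it does, the chance that at least one of the two passes at a true 5% is 0.0196 + (1 − 0.0196)(0.0196) = 0.0388, assuming independence.
3. Use the same primary objective in the synopsis and Section 1, adding *or, for RET+, the cohort's starting dose* there and in secondary objective 2.
4. If wanted, add that optional 30mg exploration leaves the FGFR1 primary set at 45mg, with 30mg reported in the by-dose summary that Section 10.3 already plans.

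The cost is wording: no added patients, no added assessments and no change to the design figures. The one consequence is under item 4: an FGFR1 group treated at 30mg by choice would be a by-dose result only, which fits the purpose that Section 4.0 gives it, namely to inform future studies.

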9.4 Dose Modifications for Adverse Drug Reactions

Dose Reduction Guidelines for Ponatinib

Dose reduction guidelines for ponatinib are summarized in Table 11 graded according to NCI CTCAE v.4.0 (Appendix D). These guidelines should be followed by clinical investigators; however, for an individual subject, dose interruptions, reductions, and treatment discontinuation should also be based on the clinical circumstance. Deviation from these guidelines must be communicated with the principal investigator. When the observed toxicity has resolved to \leq grade 1 or baseline, the investigator may resume full dosing if clinically indicated. However, in the event of an occurrence of any myocardial infarction, embolic/occlusive cerebro-vascular accident (stroke) or need for revascularization procedure, ponatinib will be permanently discontinued. In the event of any other vascular/occlusive adverse events occurring on treatment, careful consideration and documentation of a discussion with the patient relating to the benefits and risks of continuing ponatinib will be made regarding continuation of the ponatinib at any dose.

No dose reduction below 15 mg once daily is permitted for ponatinib. If the patient cannot tolerate a minimum dose of 15 mg per day of ponatinib, despite any allowed interruptions, the patient must be discontinued from study treatment. Doses may be interrupted for study-drug related toxicities for up to 28 days. If a nonhematologic study-drug related toxicity does not resolve to Grade 1 or less after dose interruption for more than 28 days, the patient must be discontinued from study treatment. If a hematologic study-drug related toxicity does not resolve to Grade 1 or less after dose interruption for more than 28 days, the Principal Investigator must be contacted. Additionally, the PI must be contacted if any adverse event deemed unrelated to treatment requires dose interruption for more than 28 days. During dose interruptions, continue to observe the study schedule as planned (i.e. days are missed not postponed).

Re-escalation following dose reduction after resolution of adverse drug reactions is permissible following discussion with the PI. Dose reductions in the event of starting doses other than 45 mg QD being taken forward will be discussed with the PI and ARIAD.

Table 11 Ponatinib: Dose Modifications for Adverse Drug Reactions Occurring at 45mg Starting Dose (30mg Starting Dose Occurrence detailed within Table)

Toxicity	Modification
Nonhematologic Toxicity	
General	
Grade 1 or transient Grade 2	No intervention
Grade 2 lasting ≥ 7 days with optimal care	
Hold ponatinib Resume at 45 mg after recovery to \leq grade 1
 
Recurrence at 45 mg: Hold ponatinib Resume at 30 mg after recovery to \leq grade 1
 
Recurrence (or Occurrence if 30mg starting dose) at 30 mg Hold ponatinib Resume at 15 mg after recovery to \leq grade 1
 
Recurrence at 15 mg Consider discontinuing ponatinib

Grade 3 or 4	
Hold ponatinib Resume at 30 mg after recovery to \leq grade 1
 
Recurrence (or Occurrence if 30mg starting dose) at 30 mg Hold ponatinib Resume at 15 mg after recovery to \leq grade 1
 
Recurrence at 15 mg Consider discontinuing ponatinib

Pancreatitis	
Grade 2 (enzyme elevation or radiologic findings only)	See amylase/lipase section below
Grade 3 (severe pain, vomiting, medical intervention indicated [eg, analgesia, nutritional support])	
Hold ponatinib Perform ultrasound or abdominal CT scan with contrast If imaging is positive, continue holding ponatinib and repeat according to clinical care If imaging is negative, or after resolution by imaging, resume at 30 mg after recovery to \leq grade 1
 
Recurrence (or Occurrence if 30mg starting dose) at 30 mg: Repeat above, except resume at 15 mg after recovery to \leq grade 1
 
Recurrence at 15 mg: Repeat above Consider discontinuing ponatinib

Toxicity	Modification
Grade 4	Discontinue ponatinib
Amylase/Lipase	
Grade \leq 2	No intervention; monitor closely
Grade 3 with no radiologic findings	
Hold ponatinib Resume at 45 mg after recovery to \leq grade 1
 
Recurrence at 45 mg: Hold ponatinib Resume at 30 mg after recovery to \leq grade 1
 
Recurrence (or Occurrence if 30mg starting dose) at 30 mg: Hold ponatinib Resume at 15 mg after recovery to \leq grade 1
 
Recurrence at 15 mg: Hold ponatinib Consider discontinuing ponatinib

Grade 3 with radiologic findings or Grade 4	
Hold ponatinib Repeat imaging according to clinical care After resolution by imaging, resume at 30 mg after recovery to \leq grade 1
 
Recurrence (or Occurrence if 30mg starting dose) at 30 mg: Repeat above Resume at 15 mg after recovery to \leq grade 1
 
Recurrence at 15 mg: Repeat above Consider discontinuing ponatinib

LV dysfunction/CHF	
Grade 2 or 3	
Hold ponatinib Resume at 45 mg after recovery to \leq grade 1
 
Recurrence at 45 mg : Hold ponatinib Resume at 30 mg after recovery to \leq grade 1
 
Recurrence (or Occurrence if 30mg starting dose) at 30 mg: Hold ponatinib Resume at 15 mg after recovery to \leq grade 1
 
Recurrence at 15 mg: Consider discontinuing ponatinib

Toxicity	Modification
Grade 4	Hold ponatinib Consider discontinuing ponatinib
Skin rash	
Grade 2 persistent despite optimal symptomatic therapy	Hold ponatinib Resume at 45 mg after recovery to \leq grade 1 Recurrence at 45 mg: Hold ponatinib Resume at 30 mg after recovery to \leq grade 1 Recurrence (or Occurrence if 30mg starting dose) at 30 mg: Hold ponatinib Resume at 15 mg after recovery to \leq grade 1 Recurrence at 15 mg: Consider discontinuing ponatinib
Grade 3 persistent despite optimal symptomatic therapy	Hold ponatinib Resume at 30 mg after recovery to \leq grade 1 Recurrence (or Occurrence if 30mg starting dose) at 30 mg: Hold ponatinib Resume at 15 mg after recovery to \leq grade 1 Recurrence at 15 mg: Consider discontinuing ponatinib
Hematologic Toxicity	
Drug-Related ANC/platelets	
Grade 1 or 2	No dose adjustment
Grade 3 or 4	Hold ponatinib Resume at 45 mg after recovery to \leq grade 1 Recurrence at 45 mg: Hold ponatinib Resume at 30 mg after recovery to \leq grade 1 Recurrence (or Occurrence if 30mg starting dose) at 30 mg: Hold ponatinib Resume at 15 mg after recovery to \leq grade 1 Recurrence at 15 mg: Consider discontinuing ponatinib

Definitions: ANC = absolute neutrophil count; CHF = congestive heart failure; CT = computed tomography; LV = left ventricular.

Recommended Dose Modifications for Hepatic Toxicity

Elevation of liver transaminase > 3 x ULN* (Grade 2 or higher)

Occurrence at 45 mg:

- Interrupt ponatinib and monitor hepatic function
- Resume ponatinib at 30 mg after recovery to ≤ Grade 1 (< 3 × ULN)

Occurrence at 30 mg:

- Interrupt ponatinib and resume at 15 mg after recovery to ≤ Grade 1

Occurrence at 15 mg:

- Discontinue ponatinib

Elevation of AST or ALT ≥ 3 x ULN concurrent with an elevation of bilirubin >2 x ULN and alkaline phosphatase < 2 x ULN

Discontinue ponatinib

*ULN = Upper Limit of Normal for the lab

